#### **Hypothesis Testing:**

The null and alternative hypotheses for superiority is as follows:  $H_0: \beta_3 \leq 0$ ,  $H_a: \beta_3 > 0$ . Superiority will be declared if the lower bound of the 2-sided 95% credible interval of the difference between Test and Control is greater than 0:  $P(\beta_3 > 0|y) \geq 0.95$ .

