### 14.2. Sample Size Justification

The plan is to enroll 60 subjects with a target of 50 subjects to complete the study. This is a pilot study and the sample size was not based on any empirical power calculation. The power analysis for different scenarios of size effects ( $\Delta$ ) and inter-subject correlation ( $\rho$ ), assuming a common VAS comfort score variance of 25, are summarized below:

Table 4: Power Analysis for VAS comfort

$\Delta$	$\rho$	Power (%)
5	.30	21.6
	.50	28.4
	.80	59.2
10	.30	64.9
	.50	79.2
	.80	99.2

The power analysis was conducted the SAS procedure PROC POWER procedure for paired tests.

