### 14.4. Level of Statistical Significance

All planned analysis for this study will be conducted with an overall type I error rate of 5%.

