#### **The Model:**

Let  $\mathbf{y}_{ijk} = (y_{1ij}, y_{2ij})^T$  denote the comfort scores for the  $i^{\text{th}}$  subject, from  $i^{\text{th}}$  site at 1week follow-up. The likelihood of  $\mathbf{y}_{ij}$  is constructed as follow:

$$\mathbf{y}_{ij} \sim N(\boldsymbol{\mu}, \boldsymbol{\Sigma}),$$

where  $\boldsymbol{\mu} = (\mu_1, \mu_2)^T$  and  $\boldsymbol{\Sigma}$  is a 2x2 variance-covariance matrix. Here  $\mu_i, i = 1, 2$ , are given by:

$$\begin{aligned}\mu_1 &= \mu_0 + \beta_1\text{BASE} + \beta_2\text{sequence} + \beta_3\text{Test}, \\ \mu_2 &= \mu_0 + \beta_1\text{BASE} + \beta_2\text{sequence} - \beta_3\text{Test},\end{aligned}$$

Other baseline characteristics such as age, gender DEQ-5 score will also be included as fixed effects when appropriate.

Non-informative prior distributions will be used for the coefficients in the models as well as for the error terms: Independent vague normal  $N(0,1000)$  priors for the regression

coefficients ( $\mu_0$  and  $\beta$ ) and inverse Wishart  $IW(R,2)$  for  $\Sigma$ .  $R$  is determined by  $S = E[\Sigma] = 4R$  where  $S$  is the sample variance-covariance matrix of the  $y_{ij}$ . The Metropolis sampler algorithm as implemented in the MCMC Procedure (SAS 9.4, SAS Institute, Cary, NC) will be used to estimate the posterior distributions of the unknown parameters. Inferences will be made based on a posterior credible interval for the relevant parameters. Results will be reported as regression coefficient mean estimates with 95% credible intervals.

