#### **14.6. Secondary Analysis**

OSDI scores will be analyzed using the same model described in the primary analysis. The null and alternative hypotheses for superiority is as follows:  $H_0: \beta_3 \geq 0$ ,  $H_a: \beta_3 < 0$ . Superiority will be declared if the upper bound of the 2-sided 95% credible interval of the difference between Test and Control is less than 0:  $P(\beta_3 < 0|y) \geq 0.95$ .

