#### **14.7. Other Exploratory Analyses**

If superiority cannot be concluded, the predictive probability of trial success (PPOS) will be calculated for different scenarios of sample size ( $n$ ) to support the planning for future studies.

Given the historical data from this pilot study, the PPOS will be estimated using a simulation based algorithm. We will simulate 1000 trials of 120 subjects from the predictive density function of  $y$ , then we will assess if success criterion  $\beta_3 > 0$  is met for each trial. The PPOS is estimated by the proportion of runs where the success criterion is met. The same algorithms will be used to calculate the PPOS for  $n = 150, 200$ .

Further exploratory analysis will be conducted on DEQ-5 scores, LipiView II® lipid layer measurements, non-invasive tear break-up time (NITBUT), corneal staining and subject's reported ocular symptoms (CTP-2009) at the discretion of the Study Responsible Clinician.

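### Sections 14.5 and 14.6 each equate two different success rules, a 2-sided 95% credible interval excluding 0 and a posterior probability of at least 0.95, and the plan does not say which governs

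*Combined protocol and SAP*

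**What the plan says.** The Hypothesis Testing paragraph of Section 14.5 sets a directional pair of hypotheses for VAS comfort (null: β₃ at or below 0; alternative: β₃ above 0). Superiority is declared if the "lower bound of the 2-sided 95% credible interval of the difference between Test and Control is greater than 0". After a colon, as though it were the same statement, comes "P(\beta_3 > 0|y) \geq 0.95".

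Section 14.6 does the same for OSDI with the sign reversed: the "upper bound of the 2-sided 95% credible interval of the difference between Test and Control is less than 0", followed by "P(\beta_3 < 0|y) \geq 0.95".

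Four other places bear on the choice:

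- **Section 14.5, The Model**, rests inference on a posterior credible interval and adds: "Results will be reported as regression coefficient mean estimates with 95% credible intervals".
- **Section 14.4** sets an overall type I error rate of 5% and gives no sidedness.
- **Section 14.2** presents Table 4, calculated for a paired test "assuming a common VAS comfort score variance of 25". It gives neither the sidedness nor the number of subjects used for the table.
- **Section 14.7** makes a further analysis depend on the outcome: "If superiority cannot be concluded, the predictive probability of trial success (PPOS) will be calculated". Its own success criterion is only that β₃ exceeds 0, with no posterior threshold.

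**The concern.** A 2-sided 95% interval leaves 2.5% in each tail, so requiring its lower bound to exceed 0 is a stricter test than requiring 95% posterior probability above 0. The sentence presents the two as equivalent, and nothing elsewhere formally ranks them.

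A result with posterior probability between 0.95 and 0.975 is then a success by the formula and a failure by the interval. The headline conclusion could be chosen after the data are seen. It would also be unclear whether the predictive-probability calculation should run, because it is conditional on superiority not being concluded.

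**Working it through.** **1. What each rule requires.** For an equal-tailed interval:

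| Rule | Posterior probability needed | Equivalent interval | Critical value, t with 49 df |
|---|---|---|---|
| 2-sided 95% interval excludes 0 | above 0.975 | 95% | 2.010 |
| Probability formula | at least 0.95 | 90% | 1.677 |

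The corresponding normal values are 1.960 and 1.645. A highest-density interval would differ little if the posterior is near-symmetric; the plan does not name the interval type. If Test is coded 1, the Test minus Control difference in the written model is 2β₃. The sign is unchanged, so the conflict remains.

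**2. Reproducing Table 4.** Inputs from Section 14.2: differences Δ of 5 and 10, and correlations ρ of 0.30, 0.50 and 0.80. Inputs inferred: n = 50 (the completion target) and SD = 25.

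- SD of the paired difference = 25 × √(2(1 − ρ)) = 29.58, 25.00 and 15.81.
- Standard error = that value ÷ √50 = 4.183, 3.536 and 2.236.
- Noncentrality = Δ ÷ standard error; power comes from the noncentral t with 49 df.
- The disputed zone is the upper-tail power at 1.677 minus the upper-tail power at 2.010.

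| Δ | ρ | Table 4 | Two-sided 5% (interval rule) | One-sided 5% (0.95 rule) | Disputed zone |
|---|---|---|---|---|---|
| 5 | 0.30 | 21.6% | 21.6% | 32.1% | 10.5% |
| 5 | 0.50 | 28.4% | 28.4% | 40.1% | 11.8% |
| 5 | 0.80 | 59.2% | 59.2% | 71.2% | 12.1% |
| 10 | 0.30 | 64.9% | 64.9% | 76.2% | 11.3% |
| 10 | 0.50 | 79.2% | 79.2% | 87.4% | 8.2% |
| 10 | 0.80 | 99.2% | 99.2% | 99.7% | 0.5% |

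The two-sided 5% test matches all six cells and the one-sided 5% test matches none. Nor does the table reproduce with n = 25, 30 or 60. Zone figures can differ by 0.1 from the difference of the rounded powers. A simulation of 200,000 trials per scenario gave zones of 10.6, 11.8, 12.0, 11.2, 8.2 and 0.5%.

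Reading the stated variance literally (SD 5) gives power of at least 99.99% under both rules and a zone of at most 0.004%, but that reading cannot produce Table 4.

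**3. Under no true difference.** Simulation at n = 50 (400,000 replicates per correlation) gave success rates of 4.9% to 5.1% under the 0.95 rule and 2.5% to 2.6% under the interval rule. The disputed zone is therefore 5% − 2.5% = 2.5%.

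**4. On the VAS scale.** At ρ = 0.50, the smallest observed difference that wins is 1.677 × 3.536 = 5.9 points under the 0.95 rule and 2.010 × 3.536 = 7.1 points under the interval rule.

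**5. In the Bayesian model itself.** The stated model, without the baseline term, was fitted to 60 deliberately borderline data sets. Seven were discordant; one had a posterior probability of 0.968 with a lower bound of −0.27.

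**6. Against the overall 5%.** For VAS alone, neither rule exceeds 5%. OSDI is tested without gating, so the chance of at least one false claim over both endpoints depends on the correlation between the two test statistics. The documents give none, so a range is assumed:

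| Assumed correlation | 0 | 0.5 | 0.7 | 0.9 |
|---|---|---|---|---|
| 0.95 rule | 9.8% | 8.8% | 8.0% | 6.8% |
| Interval rule | 4.9% | 4.5% | 4.2% | 3.5% |

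**The case against.** The strongest reply is that this is a notation slip and not an open choice. The operative words state the interval rule and the formula is a gloss after a colon. The model paragraph works with credible intervals, and Table 4 fits only a two-sided 5% test. That does make the interval rule the likelier intention. It does not settle the matter: the model paragraph does not tie the 95% level to the decision, the sidedness of Table 4 is inferred, and the same formula appears in both sections.

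One could also require both conditions, so that anything between 0.95 and 0.975 is a failure. That is a sensible conservative reading, but the plan does not state it.

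The consequence is limited, and this stands. Section 2.3 calls all hypotheses exploratory, Section 14.2 says the sample size did not come from a power calculation, and readers will see the same posterior means and 95% intervals under either rule. The zone of 8% to 12% also depends on SD 25, n = 50, a paired t-test in place of the covariate-adjusted Bayesian model, and Table 4's hypothetical effects.

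Multiplicity over VAS and OSDI is strictly a separate question. It matters here only because the two rules differ in whether they stay within the overall 5%.

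**Conclusion.** The concern holds. Both superiority claims carry a decision threshold that contradicts itself, at 0.975 against 0.95, with one-sided error of about 2.5% against 5% per endpoint. That equivalence assumes an equal-tailed interval and priors vague enough for the posterior to behave like the t distribution. The evidence leans towards the interval rule without deciding it.

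The practical effect is modest in an exploratory pilot. Still, the plan provides for a formal declaration of superiority and makes a later analysis depend on it, so the rule should be fixed before unmasking.

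**What to change.** State one rule in both sections.

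**Preferred, because it agrees with the reported 95% intervals and with Table 4:**

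- Section 14.5: superiority if the lower bound of the equal-tailed 2-sided 95% credible interval exceeds 0, that is, P(β₃ > 0 | y) > 0.975.
- Section 14.6: superiority if the corresponding upper bound is below 0, that is, P(β₃ < 0 | y) > 0.975.
- Section 14.4: add that each superiority claim is one-sided at 2.5%. Over the assumed correlations this also keeps the chance of any false claim within 5%.

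**If the sponsor prefers 0.95:**

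- Change both intervals to 90%.
- Restate Table 4 for a one-sided 5% test (32.1, 40.1, 71.2, 76.2, 87.4 and 99.7% with n = 50 and SD 25).
- Either control multiplicity across VAS and OSDI, for example by a fixed sequence, or limit the 5% in Section 14.4 to the primary endpoint.

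In either case, Section 14.7 should cite the chosen rule both for its trigger and for its success criterion. The preferred version costs two numbers, a clause in Section 14.4 and a cross-reference in Section 14.7. It needs no patients and no new data.

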#### **14.6. Secondary Analysis**

OSDI scores will be analyzed using the same model described in the primary analysis. The null and alternative hypotheses for superiority is as follows:  $H_0: \beta_3 \geq 0$ ,  $H_a: \beta_3 < 0$ . Superiority will be declared if the upper bound of the 2-sided 95% credible interval of the difference between Test and Control is less than 0:  $P(\beta_3 < 0|y) \geq 0.95$ .

#### **14.7. Other Exploratory Analyses**

If superiority cannot be concluded, the predictive probability of trial success (PPOS) will be calculated for different scenarios of sample size ( $n$ ) to support the planning for future studies.

Given the historical data from this pilot study, the PPOS will be estimated using a simulation based algorithm. We will simulate 1000 trials of 120 subjects from the predictive density function of  $y$ , then we will assess if success criterion  $\beta_3 > 0$  is met for each trial. The PPOS is estimated by the proportion of runs where the success criterion is met. The same algorithms will be used to calculate the PPOS for  $n = 150, 200$ .

Further exploratory analysis will be conducted on DEQ-5 scores, LipiView II® lipid layer measurements, non-invasive tear break-up time (NITBUT), corneal staining and subject's reported ocular symptoms (CTP-2009) at the discretion of the Study Responsible Clinician.

#### **14.8. Interim Analysis**

No interim analysis is planned.

#### **14.9. Procedure for Handling Missing Data and Drop-Outs**

Missing or spurious values will not be imputed. The count of missing values will be included in the summary tables and listings.

#### **14.10. Procedure for Reporting Deviations from Statistical Plan**

The analysis will be conducted according to that specified in above sections. There are no known reasons for which it is planned to deviate from these analysis methods. If for any reason a change is made, the change will be documented in the study report along with a justification for the change.

## **15. DATA HANDLING AND RECORD KEEPING/ARCHIVING**

### **15.1. Electronic Case Report Form/Data Collection**

The data for this study will be captured on electronic case report forms (eCRFs) using an EDC system (Bioclinica). An authorized data originator will enter study data into the eCRFs using the EDC system. Data collected on equipment that is not captured in EDC will be formatted to the specification of the JJV database manager and sent to JJV for analysis.

External Date Sources for this study include: Not Applicable

The clinical data will be recorded on dedicated eCRFs specifically designed to match the study procedures for each visit. Once completed, the eCRFs will be reviewed for accuracy and completeness and signed by the Investigator. The sponsor or sponsor's representatives will be authorized to gain access to the subject recordation for the purposes of monitoring and auditing the study.

Edit checks, electronic queries, and audit trails are built into the system to ensure accurate and complete data collection. Data will be transmitted from the clinical site to a secure central database as forms are completed or updated, ensuring information accuracy, security, and confidentiality. After the final database lock, the Investigator will be provided with Individual Patient Profiles (IPP) including the full audit trail on electronic media in PDF format for all of the study data. The IPP must be retained in the study files as a certified copy of the source data for the study.

The content and structure of the eCRFs are compliant with ISO14155:2011.

### **15.2. Subject Record**

At a minimum, subject record should be available for the following:

- subject identification
- eligibility
- study identification
- study discussion
- provision of and date of informed consent
- visit dates
- results of safety and efficacy parameters as required by the protocol
- a record of all adverse events
- follow-up of adverse events
- medical history and concomitant medication
- test article receipt/dispensing/return records
- date of study completion
- reason for early discontinuation of test article or withdrawal from the study, if applicable

The subject record is the eCRF or an external record. The author of an entry in the subject record must be identifiable. The first point of entry is considered to be the source record.

Adverse event notes must be reviewed and initialed by the Investigator.

## **16. DATA MANAGEMENT**

### **16.1. Access to Source Data/Document**

The Investigator/Institution will permit trial-related monitoring, audits, IEC/IRB review and regulatory inspection(s) by providing direct access to source data/documents. Should the clinical site be contacted for an audit by an IEC/IRB or regulatory authority, JJV must be contacted and notified in writing within 24 hours.

### **16.2. Confidentiality of Information**

Information concerning the investigational product and patent application processes, scientific data or other pertinent information is confidential and remains the property of JJV. The Investigator may use this information for the purposes of the study only. It is understood by the Investigator that JJV will use information developed in this clinical study in connection with the development of the investigational product and therefore may disclose it as required to other clinical investigators and to regulatory agencies. In order to allow the use of the information derived from this clinical study, the Investigator understands that he/she has an obligation to provide complete test results and all data developed during this study to the Sponsor.

### **16.3. Data Quality Assurance**

Steps will be taken to ensure the accuracy and reliability of data, include the selection of qualified investigators and appropriate clinical sites and review of protocol procedures with the Principal Investigator. The Principal Investigator, in turn, must ensure that all Sub-Investigators and clinical site personnel are familiar with the protocol and all study-specific procedures and have appropriate knowledge of the study article.

Training on case report form completion will be provided to clinical site personnel before the start of the study. The Sponsor will review case report forms for accuracy and completeness remotely during the conduct of the study, during monitoring visits, and after transmission to data management. Any data discrepancies will be resolved with the Investigator or designee, as appropriate.

Quality Assurance representatives from JJV may visit clinical sites to review data produced during the study and to access compliance with applicable regulations pertaining to the conduct of clinical trials. The clinical sites will provide direct access to study-related source data/documents and reports for the purpose of monitoring and auditing by JJV and for inspection by local and regulatory authorities.

## **17. MONITORING**

The study monitors will maintain close contact with the Principal Investigator and the Investigator's designated clinical site personnel. The monitor's responsibilities will include:

- Ensuring that the investigation is being conducted according to the protocol, any subsequent amendments, and regulatory requirements are maintained
- Ensuring the rights and wellbeing of subjects are protected
- Ensuring adequate resources, including facilities, laboratories, equipment, and qualified clinical site personnel

- Ensuring that protocol deviations are documented with corrective action plans, as applicable
- Ensuring that the clinical site has sufficient test article and supplies
- Clarifying questions regarding the study
- Resolving study issues or problems that may arise
- Reviewing of study records and source documentation verification in accordance with the monitoring plan

## **18. ETHICAL AND REGULATORY ASPECTS**

### **18.1. Study-Specific Design Considerations**

Potential subjects will be fully informed of the risks and requirements of the study and, during the study, subjects will be given any new information that may affect their decision to continue participation. Subjects will be told that their consent to participate in the study is voluntary and may be withdrawn at any time with no reason given and without penalty or loss of benefits to which they would otherwise be entitled. Only subjects who are fully able to understand the risks, benefits, and potential adverse events of the study, and provide their consent voluntarily will be enrolled.

### **18.2. Investigator Responsibility**

The Principal Investigator is responsible for ensuring that the clinical study is performed in accordance with the signed agreement, the investigational plan, Section 4 of the ICH E6 guidelines on Good Clinical Practice (GCP), and applicable regulatory requirements. GCP is an international ethical and scientific quality standard for designing, conducting, recording, and reporting studies that involve the participation of human subjects. Compliance with this standard provides public assurance that the rights, safety, and well-being of study subjects are protected, consistent with the principles of the Declaration of Helsinki 64th WMA General Assembly 2013 and that the clinical study data are credible. The Investigator must maintain clinical study files in accordance with Section 8 of the ICH E6 guidelines on Good Clinical Practice (GCP), and applicable regulatory requirements.

### **18.3. Independent Ethics Committee or Institutional Review Board (IEC/IRB)**

Before the start of the study, the Investigator (or Sponsor when applicable) will provide the IEC/IRB with current and complete copies of the following documents (where applicable):

- Final protocol and, if applicable, amendments
- Sponsor-approved informed consent form (and any other written materials to be provided to the subjects)
- Investigator's Brochure (or equivalent information) and amendments
- Sponsor-approved subject recruitment materials
- Information on compensation for study-related injuries or payment to subjects for participation in the study
- Investigator's curriculum vitae, clinical licenses, or equivalent information (unless not required, as documented by IEC/IRB)
- Information regarding funding, name of the Sponsor, institutional affiliations, other potential conflicts of interest, and incentives for subjects
- Any other documents that the IEC/IRB requests to fulfill its obligation

This study will be undertaken only after IEC/IRB has given full approval of the final protocol, amendments (if any), the informed consent form, applicable recruiting materials, and subject compensation programs, and the Sponsor has received a copy of this approval. This approval letter must be dated and must clearly identify the documents being approved.

During the study, the Investigator (or Sponsor when applicable) will send the following documents to the IEC/IRB for their review and approval, where appropriate:

- Protocol amendments
- Revision(s) to informed consent form and any other written materials to be provided to subjects
- If applicable, new or revised subject recruitment materials approved by the Sponsor
- Revisions to compensation for study-related injuries or payment to subjects for participation in the study
- Investigator's Brochure amendments or new edition(s)
- Summaries of the status of the study (at least annually or at intervals stipulated in guidelines of the IEC/IRB)
- Reports of adverse events that are serious, unanticipated, and associated with the test articles, according to the IRB's requirements
- New information that may adversely affect the safety of the subjects or the conduct of the study
- Major protocol deviations as required by the IEC/IRB
- Report of deaths of subjects under the Investigator's care
- Notification if a new Investigator is responsible for the study at the clinical site
- Any other requirements of the IEC/IRB

For protocol amendments that increase subject risk, the amendment and applicable informed consent form revisions must be submitted promptly to the IEC/IRB for review and approval before implementation of the change(s).

At least once a year, the IEC/IRB will review and reapprove this clinical study. This request should be documented in writing.

At the end of the study, the Investigator (or Sponsor where required) will notify the IEC/IRB about the study completion. Documentation of this notification must be retained at the clinical site and a copy provided to the CRO or Sponsor as applicable.

